### **3.0 ELIGIBILITY:**

#### **3.1 Inclusion Criteria:**

3.1.1 Pathologically or cytologically confirmed NSCLC

3.1.2 Stage IIIB or stage IV.

3.1.3 Patient to meet either criterion A or B:

A) Patient must have progressed after at least 1 line of systemic treatment (IV or oral) for metastatic or locally advanced disease. Must provide documentation systemic treatment was for either locally advanced or metastatic. Must also provide scan or assessment to show most recent progression, pre-enrollment certifying progression of disease to meet inclusion eligibility of progression. Radiation does not count as 1 line.

FDA exemption 6/30/15, 6/30/15, 8/17/15 (for LOCR initial), Amendment #1 10/5/15 v 2 HS approval, Amendment # 2 11/9/15, Amendment #3 3/4/16, Amendment # 4 4/7/16, Amendment # 5 6/1/16 V2, Amendment # 6 7/7/16, Amendment # 7 11/16/16, Amendment # 8 2/22/17, Amendment #9 5/22/17

B) Patients progressing within 6 months of completion of neoadjuvant or adjuvant chemotherapy are also eligible without having treatment for metastatic disease (for example patient with stage I disease undergoes resection, receives systemic chemotherapy and then progresses to the liver (now stage IV) within 6 months of chemotherapy). Radiation does not count as 1 line.

3.1.4 Ablation for advanced lung cancer is being considered by the treating physician for treatment or prevention of symptoms such as pain, bleeding or obstruction- Documentation is required in writing by MD for this criterion.

3.1.5 At least 1 site of measurable disease that will not be treated with ablation. Sites to send confirmation on which lesion of measurable disease will not be ablated for tracking of response.

3.1.6 At least 3 weeks since prior systemic treatment and/or radiation therapy for patient's NSCLC (from treatment day 1 on study)

3.1.7. No brain metastases except for patients whose metastases have been removed by surgical resection or have had stereotactic radiation or gamma knife with no evidence of active disease on MRI within 28 days of starting treatment.

3.1.8. Eastern Cooperative Oncology Group (ECOG) Performance Status of 0-2.

3.1.9. Life expectancy of at least 12 weeks.

3.1.10. Required entry laboratory parameters within 14 days of study entry: Granulocytes  $\geq$  1000/ $\mu$ l; platelet count  $\geq$ 75,000/ $\mu$ l; Creatinine  $\leq$  1.5x upper limit normal mg/dl; Bilirubin  $<$  1.5x upper limit normal; AST  $\leq$  3 x upper limit of normal.

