#### **5.0 DOSE MODIFICATIONS OF NIVOLUMAB AND TOXICITY MANAGEMENT:**

Adverse events will be graded with the use of the National Cancer Institute Common Terminology Criteria for Adverse Events, version 4

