## **5.1 Nivolumab Dose Modifications:**

No dose reductions of nivolumab are included in the study. Any adverse event, laboratory abnormalities, or undercurrent illness which in the judgment of the investigator, can warrant delaying the dose of study medication.

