## **5.2 The following must be confirmed prior to dosing a patient with Nivolumab:**

- 1) Patients experiencing treatment related (drug) grade 4 or treatment related (drug) clinically significant grade 3 toxicities must have toxicity resolved to grade 2 or less prior to resuming nivolumab.

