## **5.3 Hold treatment until recovery to grade 1 or resolution for:**

- 1) If AST or ALT >3 to 5 times ULN (grade 2) or total bilirubin >1.5 to 3 times ULN (grade 2): **Withhold treatment**; may resume therapy upon recovery to grade 0 or 1 toxicity (AST/ALT grade 1 is >ULN-3xULN, Total bilirubin grade 1 is >ULN-1.5xULN).

\*\*for possibly, probably or definitely related to nivolumab see section 5.3, 2.I below

\*\*AST or ALT >5 times ULN (grade 3) or total bilirubin >3 times ULN (grade 3) or severe/life-threatening immune-mediated hepatitis: **Permanently discontinue**. \*\*see section 5.3 (this section), 2\*\* below

- 2) Immune-mediated hepatitis:

- I. Grade 2 or higher transaminase elevations that are possibly, probably or definitely related to nivolumab (with or without total bilirubin elevations): Withhold treatment and initiate high-dose systemic corticosteroids (prednisone 1 to 2 mg/kg daily or equivalent)

\*\* Severe (grade 3) or life-threatening (grade 4) transaminase elevations: Permanently discontinue treatment and initiate high-dose systemic corticosteroids (prednisone 1 to 2 mg/kg daily or equivalent)

- 3) **Colitis:**

- I.** Grade 2 (duration >5 days): Also administer systemic corticosteroids (prednisone 0.5 to 1 mg/kg daily or equivalent) followed by a corticosteroid taper; may increase to prednisone 1 to 2 mg/kg daily (or equivalent) if colitis worsens or does not improve despite corticosteroid use
- II.** Grade 3: Also administer systemic corticosteroids (prednisone 1 to 2 mg/kg daily or equivalent) followed by a corticosteroid taper

- 4) **Pneumonitis:** Pneumonitis (grade 2); also administer high-dose systemic corticosteroids (prednisone 1 to 2 mg/kg daily or equivalent) followed by a corticosteroid taper

- 5) **Other immune-mediated toxicities:** Other immune-mediated toxicities; also administer high-dose systemic corticosteroids followed by a corticosteroid taper (over 1 month)

- 6) **Creatinine** >1.5 to 6 times ULN (grade 2 or 3) or >1.5 times baseline (grade 1): Withhold treatment; administer prednisone 0.5 to 1 mg/kg daily (or equivalent) followed by a corticosteroid taper; may resume therapy upon recovery to grade 0 or 1 toxicity. If toxicity worsens or does not improve, permanently discontinue and increase corticosteroid dose to prednisone 1 to 2 mg/kg daily (or equivalent).

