#### 6.0 SCHEDULE OF EVALUATIONS / STUDY CALENDAR

Parameter	Pre-study (to be sent to BrUOG prior to registration)	Within 3 days prior to Day 1 of Each Cycle of Nivolumab (approximately every 2 weeks) F	While on Nivolumab therapy (Every 12 weeks approximately every 6 cycles)	Ablation L Cycles 1(1 week after starting drug) and prior to each additional ablation (if performed)	End of Treatment (2 week window provided)	30 days post last dose of drug	FU D
Informed Consent (within 30 days of day 1) *pts are to be re-consented if ICF will be outside 30 day window	X						
Demographics	X						
Conmed log P	X	X	X	X	X		
Nivolumab K		X					
Optional labs: 3, 6ml purple top tubes to [name] at RIH at multiple time points	X	X O		X O			X O
Optional Tissue biopsy				X M			
History G	X			X			
Physical examination	X	X Q			X	X I	
Weight	X	X					
Vital signs	X	X					
Toxicity Assessment	X	X			X	X H	
Performance Status	X	X			X		
CBC, diff, platelet count	X (within 14 days)	X			X		
Na, K, BUN, Cr, AST, ALT, Bili	X (within 14 days)	X			X		
Ca, Mg, PO4	X (within 14 days)	X			X		
INR, TSH	X (within 14 days)						
Pre-Ablation labs: PLT, PT, PTT, INR				(within 2 weeks of ablation up to day of (prior to) N			

Serum Pregnancy E	X (within 7 days of drug)						
CT scan of Chest/abd/pelvis	X AC (with in 6 weeks)		X CJ		X CJ (CT does not need to be repeated if done in prior 2 months)		X D
CT scan or MRI of brain	X(within 6 weeks)		X (only if clinically indicated)		X (only if clinically indicated)		X
EKG B	X						
Survival and Disease status						X	X D

A- CT Scan for disease assessment to be performed within 6 weeks of study entry. Report required. (chest X-ray okay with baseline).

B- EKG within 8 weeks of study entry. Report required

C- An MRI or PET scan may substitute for disease assessment.

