### ***DOSAGE FORMS AND STRENGTHS***

Injection: 40 mg/4 mL (10 mg/mL) and 100 mg/10 mL (10 mg/mL) solution in a single-use vial.

Dosage: Subjects will be treated with 3mg/kg up to a maximum dose of 240mg of nivolumab as an approximate 60 minute IV infusion every 2 weeks.

Immuno-oncology (I-O) agents are associated with adverse events that can differ in severity and duration than adverse events caused by other therapeutic classes. Nivolumab is considered an immuno-oncology agent in this protocol. Early recognition and management of adverse events associated with immuno-oncology agents may mitigate severe toxicity. Immune Toxicities may include:

- Pulmonary (pneumonitis)
- Gastrointestinal (colitis with diarrhea)
- Endocrinopathies (including inflammation of the thyroid, adrenal and pituitary)
- Hepatic (hepatitis)
- Renal (nephritis)
- Skin (rash)
- Neurological (neuritis)

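### Protocol 5.3(6): the creatinine hold trigger at 1.5 times baseline carries a grade label that already permits restart

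*Protocol*

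**What the plan says.** Protocol 5.3(6) gives two reasons to hold nivolumab and start prednisone at 0.5 to 1 mg/kg daily:

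- creatinine above 1.5 and up to 6 times ULN, labelled grade 2 or 3;
- creatinine raised relative to the patient's own baseline: "or >1.5 times baseline (grade 1): Withhold treatment".

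The restart and stop conditions then follow once, for both triggers: "may resume therapy upon recovery to grade 0 or 1 toxicity. If toxicity worsens or does not improve, permanently discontinue". The permanent stop comes with an increase in prednisone to 1 to 2 mg/kg daily. The heading of 5.3 likewise sets recovery to grade 1, or resolution, as the end of a hold. No restart level relative to baseline appears anywhere.

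Four other places bear on the point:

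- Section 5.0 names the grading standard: "Adverse events will be graded with the use of the National Cancer Institute Common Terminology Criteria for Adverse Events, version 4". The creatinine limits of that standard are not reproduced beyond the labels in 5.3(6) and 5.4(6).
- Section 3.1.10 admits patients with creatinine up to "1.5x upper limit normal mg/dl".
- The study calendar in Section 6.0 lists "Na, K, BUN, Cr, AST, ALT, Bili" before each cycle.
- Section 5.1 leaves the investigator free to hold: adverse events and laboratory abnormalities "can warrant delaying the dose of study medication".

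**The concern.** A hold rule needs a restart level that the patient does not already meet when the hold begins. The other entries in 5.3 that state a grade satisfy this. For AST, ALT and bilirubin in 5.3(1), the trigger is grade 2, restart is at grade 0 or 1, and the upper limit of grade 1 is written out in multiples of ULN. The baseline creatinine trigger is the exception, because its label is grade 1 and grade 1 is also the restart grade.

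The grade therefore cannot separate a patient who is ready to restart from one who should stay on hold, or from one who has not improved and must stop for good with a higher steroid dose. Section 9.0 names nephritis among the immune toxicities of nivolumab, so this rule may well be used. Under footnote Q of the study calendar, a physician visit is required only every other cycle. At the cycles between, the written laboratory rule carries more of the decision.

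**Working it through.** The plan gives no numerical figure on this point to reproduce. The check compares the hold and restart ranges, with creatinine in multiples of ULN so that no laboratory value has to be assumed.

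**Inputs**
- Baseline trigger: creatinine > 1.5 x baseline, labelled grade 1 (5.3(6)).
- ULN trigger: creatinine > 1.5 x ULN, labelled grade 2 or 3 (5.3(6)).
- Restart: grade 0 or 1 (5.3(6)).
- Baseline allowed at entry: up to 1.5 x ULN (3.1.10).
- Assumption: grade 1 extends up to the point where the ULN trigger begins. 5.3(6) shows where the grade 1 label starts but states no upper limit for it.

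**Formula.** Let b = baseline / ULN. The baseline trigger starts at 1.5b. Under the assumption, the restart grade runs up to 1.5. The range that is both hold and restart is from 1.5b to 1.5. Its width is 1.5 - 1.5b = 1.5(1 - b), which is positive only when b < 1.

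| b (illustrative) | Baseline trigger, 1.5b (x ULN) | Overlap (x ULN) | Width |
|---|---|---|---|
| 0.5 | 0.75 | 0.75 to 1.50 | 0.75 |
| 0.6 | 0.90 | 0.90 to 1.50 | 0.60 |
| 0.7 | 1.05 | 1.05 to 1.50 | 0.45 |
| 0.8 | 1.20 | 1.20 to 1.50 | 0.30 |
| 0.9 | 1.35 | 1.35 to 1.50 | 0.15 |
| 1.0 | 1.50 | none | 0 |
| 1.2 | 1.80 | none | 0 |
| 1.5 (entry limit) | 2.25 | none | 0 |

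At b = 1.0 the two triggers coincide. Above that, the ULN trigger is reached first.

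**One patient followed through.** Take b = 0.8 and an on-treatment creatinine of 1.30 x ULN. Relative to baseline this is 1.30 / 0.8 = 1.625, above 1.5, so the drug is held. Relative to ULN it is below 1.5, so the only label is grade 1.

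- *Unchanged at the next check (1.30 x ULN).* The grade is 1, which is the restart grade. The value is still above 1.5 x baseline, which is the hold trigger. It has not improved, which is the permanent-stop condition.
- *Slightly lower at the next check (1.25 x ULN).* Relative to baseline this is 1.25 / 0.8 = 1.5625. It has improved and is labelled grade 1, so restart is allowed. It is still above 1.5 x baseline, so the hold applies too.

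**What depends on the assumption.** Only the upper end of the overlap does. If the printed label is right, a value just above 1.5 x baseline is grade 1 for any b < 1, so the conflict exists at the lower end. If CTCAE version 4 assigns another grade, the error is the label and the table does not apply.

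**The case against.** The strongest reply is that the text can be worked with. Restart is permitted, not required, and only on recovery; an unchanged value is not a recovery. The stop sentence is an instruction, so an unchanged value falls under it. The hold trigger is a standing condition checked before every cycle, so a patient still above 1.5 x baseline would be held again. Section 5.1 adds investigator discretion. Together these lean towards holding.

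Most of that stands. A reader might infer that the protocol leaves a site with no usable rule, or tells it to re-dose an unresolved rise. The documents support neither reading. What the reply does not settle is the patient who has improved but remains above 1.5 x baseline: this is a recovery of sorts, at the restart grade, with the hold trigger still met. The level that the reply arrives at has to be inferred, and it differs from the grade that is written.

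Two other inferences go too far. From the table, a reader might say that creatinine at three times baseline (1.50 / 0.5) still carries the restart grade. That needs grade 1 to have no cap below the ULN trigger, which 5.3(6) does not state. A reader might also see a contradiction with 5.2, where a patient with serious drug-related toxicity "must have toxicity resolved to grade 2 or less prior to resuming nivolumab". That is a minimum for grade 3 and 4 events. It can be met together with the stricter rules in 5.3, 5.4, 5.5 and 5.7, and it does not reach a trigger labelled grade 1.

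**Conclusion.** The point holds as a minor safety-wording correction. On the protocol's own labels, the baseline creatinine trigger lies inside its own restart range, and an unchanged value also meets the permanent-stop condition. It affects only patients with baseline creatinine below ULN. The band from 1.5 x baseline to 1.5 x ULN rests on the assumption that grade 1 extends up to the ULN trigger. Whether the grade label is itself correct cannot be settled from the documents.

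The documents give no rate of creatinine rise and no distribution of baseline values, so the number of patients affected cannot be estimated. A cautious site would probably keep holding. A reader might suspect an effect on the trial's statistics, but the Simon design (18 then 33 patients, at least 5 responses to continue and 11 to reject the null) and the analysis do not depend on this rule.

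**What to change.** In 5.3(6), replace the grade-based restart with a level: nivolumab may resume only when neither hold trigger is met, that is, when creatinine is at or below 1.5 x baseline and also at or below 1.5 x ULN. Stating both limits settles which one governs a patient who met both triggers. In the notation above, the restart ceiling becomes 1.5 x the smaller of b and 1, so the overlap disappears at every baseline. Check the grade 1 label against CTCAE version 4 at the same time and correct it if needed. The restart level works whichever way that check comes out.

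The cost is a short amendment with IRB approval, plus a clinical consequence that the sponsor should accept knowingly. Some patients will be held longer and may miss doses, including those recovering from grade 2 or 3 creatinine whose baseline is below ULN. At a baseline of 0.8 x ULN, for example, the restart ceiling moves from 1.50 x ULN (under the assumption above) to 1.5 x 0.8 = 1.20 x ULN. The exact level is a clinical choice that the documents do not make. The one proposed here is the level at which the protocol's own hold triggers cease to apply.

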## **4.0 TREATMENT:**

**4.1 Nivolumab:** 3mg/kg up to a maximum dose of 240mg IV over approximately 60 minutes on Day 1 +/- 3 days every 2 weeks until progression for a maximum of 2 years.

It will also not be considered a deviation if a cycle or pre-cycle assessment must be adjusted to accommodate scheduling or holidays. Adjustment must be documented with reason to BrUOG. While efforts should be made to have cycles be every 2 weeks (+/- 3 days), further allowances are allowed as long as cycles are not < 10 days.

**4.2 Ablation:** Either cryoablation or thermal ablation may be performed as per standard institutional policies. Ablation should be performed within 1 week (7 days) of the initial treatment with nivolumab, to occur within the first cycle (14 days) of treatment. Additional ablation procedures may be performed as clinically indicated such as for pain control including the treatment or prevention of pain or obstruction or as per institutional standard of care. There must be a minimum of 60 days between each ablation (60-90 days is preferable). Standard institutional procedures may be used in ablation. One or more than one lesion may undergo ablation as per investigator judgement and institutional standard of care. At least one measurable site of disease cannot be ablated so that it may be followed for response. This location should be chosen at baseline with enrollment-see section 3.1.5

During the same procedural period as ablation, if patient has consented and agreed, a tumor tissue biopsy may be obtained prior to each ablation, as per institutional standard of care. This biopsy may be assessed for future correlative studies such as assessment of PD-L1 by immunohistochemical staining and will allow for correlation to response.

The following treatments must not be administered during the study: Immunotherapy other than the study drug, immunosuppressive drugs [i.e., chemotherapy or systemic corticosteroids except for short term treatment of allergic reactions or for the treatment of immune related adverse events (irAEs)}, or other experimental pharmaceutical products. Short term administration of systemic steroid (i.e., for allergic reactions or the management of irAEs is allowed).

Growth factors (granulocyte colony stimulating factor or granulocyte macrophage colony stimulating factor). Exception: Erythropoietin and darbepoietin alpha may be prescribed at the investigator's discretion.

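### Protocol 5.3(6) orders prednisone on a creatinine value alone, without the immune-mediated or drug-related condition that would make it consistent with 4.2

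*Protocol*

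**What the plan says.** Protocol 5.3(6) has two creatinine triggers: more than 1.5 and up to 6 times ULN, labelled grade 2 or 3, and a limb relative to baseline, ">1.5 times baseline (grade 1): Withhold treatment". For either one the order is "Withhold treatment; administer prednisone 0.5 to 1 mg/kg daily (or equivalent) followed by a corticosteroid taper". The item then continues: "may resume therapy upon recovery to grade 0 or 1 toxicity. If toxicity worsens or does not improve, permanently discontinue and increase corticosteroid dose", the increased dose being 1 to 2 mg/kg daily.

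Protocol 4.2 introduces its list of barred treatments with "The following treatments must not be administered during the study". The list includes "systemic corticosteroids except for short term treatment of allergic reactions or for the treatment of immune related adverse events".

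The liver rules in the same section are built differently. 5.3(1) holds nivolumab on a grade 2 laboratory value of any cause and adds a pointer: "for possibly, probably or definitely related to nivolumab see section 5.3, 2.I below". The steroid rule it points to, 5.3(2)(I), covers "Grade 2 or higher transaminase elevations that are possibly, probably or definitely related to nivolumab".

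**The concern.** Creatinine can rise for reasons unrelated to immune activation; dehydration and obstruction are ordinary examples. Nothing in 5.3(6) separates such a rise from immune nephritis. A site that judges a rise to be non-immune then faces two instructions. If it gives prednisone, it departs from 4.2. If it withholds prednisone, it departs from the wording of 5.3(6).

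The first stake is patient safety: an immunosuppressive dose for someone with no immune event to treat. The second is consistent conduct across sites, since two sites with the same patient could act in opposite ways and each cite the protocol. The protocol otherwise tries to keep immunosuppression out. Exclusion 3.2.3 does this at entry and the 4.2 list does it on study.

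**Working it through.** The point rests mainly on comparing the texts. The plan states no figure to reproduce.

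**Step 1. What triggers a steroid in each item of 5.3.**

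| Item | Trigger for steroid | Limited to drug-related or immune events? |
|---|---|---|
| 5.3(2)(I) transaminases, grade 2 or higher | Laboratory value plus relatedness | Yes, by heading and by wording |
| 5.3(3) colitis | Named clinical toxicity | No attribution wording, but a clinical diagnosis |
| 5.3(4) pneumonitis | Named clinical toxicity | No attribution wording, but a clinical diagnosis |
| 5.3(5) other toxicities | Immune-mediated toxicity | Yes, by wording |
| 5.3(6) creatinine | Laboratory value only | No |

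5.3(6) is the only item in 5.3 in which a laboratory value triggers a steroid with neither attribution wording nor an immune-mediated heading.

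**Step 2. Comparison with 4.2.**
- Immune nephritis: 5.3(6) orders prednisone and 4.2 allows it under the immune-related exception. There is no conflict.
- Non-immune rise: 5.3(6), read literally, orders prednisone and neither exception in 4.2 applies. The two conflict.

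**Step 3. Size of the order.** Dose = weight × mg/kg. The weights are assumed; the mg/kg figures are from 5.3(6).

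| Weight | Start, 0.5 to 1 mg/kg | If worse or not improved, 1 to 2 mg/kg |
|---|---|---|
| 60 kg | 30 to 60 mg/day | 60 to 120 mg/day |
| 80 kg | 40 to 80 mg/day | 80 to 160 mg/day |
| 100 kg | 50 to 100 mg/day | 100 to 200 mg/day |

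**Step 4. How easily the triggers are met.**
- Baseline limb: the trigger lies inside the normal range when 1.5 × baseline < 1 × ULN, that is, when baseline < 1/1.5 = 0.67 × ULN. Example (assumed): with baseline 0.6 × ULN the trigger is 1.5 × 0.6 = 0.90 × ULN. A value of 0.95 × ULN is 0.95/0.6 = 1.58 times baseline, so it qualifies while still normal.
- ULN limb: 3.1.10 admits patients with creatinine up to 1.5 × ULN, which is where this limb begins. A patient entering at 1.4 × ULN (assumed) qualifies at 1.51 × ULN, a rise of 1.51/1.4 − 1 = 8%.

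**Step 5. Restart level of the baseline limb.** The trigger is labelled grade 1 and restart is allowed at grade 0 or 1. The grade therefore cannot say when a patient who met only this limb has recovered, and no creatinine value is given in its place.

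**Step 6. Related lines in 5.4.** 5.4(6) orders high-dose steroids for creatinine above 6 times ULN, again without attribution wording. 5.4(7) repeats the grade 3 and 4 transaminase line of 5.3(2) without the immune-mediated hepatitis heading above it there. Both end nivolumab and take the patient off study, so 4.2 bears less on them.

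**The case against.** The strongest reply is that immune nephritis was obviously meant. Section 5.0 concerns toxicity management. Item 6 comes directly after the immune toxicities and itself speaks of toxicity recovering or worsening. Section 9.0 lists nephritis among the immune toxicities. The protocol also uses a laboratory grade as shorthand for an immune event elsewhere: 5.5 gives steroids for grade 2 or higher transaminases with no relatedness phrase, under an immune-mediated hepatitis heading. On that reading the exception in 4.2 applies and nothing conflicts. This stands as the likely intent, and it rules out the inference that the protocol deliberately orders steroids for every cause. But 5.3(6) has neither the phrase nor the heading, so the intent has to be supplied by the reader.

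Three further limits also stand:
- A reader might infer that 5.3(6) is unusual in letting nivolumab restart with no steroid dose to be reached first. It is not. Items 2(I), 3, 4 and 5 name none either, and the backstop in 5.4(4), 10 mg/day or less within 12 weeks, covers them all.
- A reader might infer that an unchanged value on the baseline limb both permits restart and requires discontinuation. The item and the 5.3 heading require recovery, which implies improvement. What remains is an unclear restart level.
- The documents give no rate of non-immune creatinine rises, so the number of patients affected cannot be estimated.

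It can also be said that possible relatedness is a low threshold, so the amendment may spare few patients. That is fair, but it would still spare those whose rise has a clear other cause, and it removes the conflict with 4.2.

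**Conclusion.** The point holds as a drafting error with a safety consequence. 5.3(6) makes prednisone mandatory on a creatinine value alone, at 0.5 to 1 mg/kg and then 1 to 2 mg/kg, and omits the condition that the grade 2 liver rule states. For a rise judged non-immune, the literal order conflicts with 4.2. The restart level of the baseline limb is a smaller, separate ambiguity.

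The size per patient is 40 to 80 mg of prednisone daily at an assumed 80 kg, possibly with creatinine still in the normal range. The size across the trial is unknown. The conclusion rests on reading the item as written; if every site reads nephritis into it, no harm follows. Taking steroid and resumed nivolumab together is permitted, not ordered. Nothing in section 17 or the SAP depends on this item, so error rates and sample size are unaffected. It should be corrected because the change is cheap and the literal order can harm a patient.

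**What to change.** In 5.3(6):
- Keep the hold for a rise of any cause. 5.1 already lets a laboratory abnormality delay a dose.
- Make both steroid doses conditional on suspected immune-mediated nephritis, using the three-level relatedness wording of 5.3(2)(I).
- For other causes, work up and treat the cause, with no mandated steroid.
- State a restart level for the baseline limb, for example creatinine back to 1.5 times baseline or less.

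For consistency, add the same condition to 5.4(6) and restore the immune-mediated hepatitis limit in 5.4(7). Section 5.5 needs no change, because its heading already supplies the limit.

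The cost is a short text amendment. Sites already make this judgement for liver rises, and 11.3 requires a relationship assessment for every adverse event. The Yes/No guidance in 11.4 has no level for possible relatedness, so the amendment must state the threshold itself. The downside is a delay in steroids if an immune event is misjudged as unrelated; the low threshold limits that risk.
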